1.2 Schema

We will undertake a single arm feasibility study with n=20 patients with treatment naïve biopsy proven ILC who have either: a) clinical or imaging suspicion of metastatic disease; b) biopsy proven metastatic disease but in whom there is suspicion of an even greater tumor burden that could change therapy approach. All patients will be recruited from the Winship Glenn Family Breast Cancer Program at any Emory facility and they will have already undergone best standard of care conventional imaging (CT or MR and possibly bone scan depending on clinical presentation). **Standard of care conventional imaging typically does not include FDG PET, since FDG PET is not recommended for lobular cancer due to low sensitivity.** We will then complete both fluciclovine PET and Ga PSMA PET scans on the same patient on separate days separated by at least 10 half-lives to allow for radioactive decay. There is no need for randomization since each patient will undergo both imaging techniques, and the results will be interpreted blindly. Thus, radiopharmacy scheduling will dictate the order of the radiotracers to ensure the patient will undergo both imaging modalities in the shortest time frame. Sometimes this will mean PSMA is completed first, followed by fluciclovine, and other times the opposite. After interpretation of both studies, careful correlation to already obtained conventional imaging will then be done to determine if a previously unsuspected anatomic correlate can be identified which would impact therapy. One or two metastases (depending on scan findings) will then undergo biopsy in the safest manner possible as standard of care (if not already done) to determine the verified detection rate of metastatic disease. Uncommonly, definitive imaging such as MR for skeletal or liver lesions may be accepted in lieu of biopsy, if biopsy is not feasible. We will then compare verified detection rate of each PET study to conventional imaging and to each other. In addition, we will collect peripheral blood for ctDNA in all patients and determine if ctDNA correlates with presence or absence of metastases and tumor burden as identified by conventional imaging, fluciclovine and/or PSMA PET. Study Specific Experimental Procedures will only consist of both PET studies and ctDNA analysis. All other procedures will be conducted per standard of care. See Figure 1.

Figure 1: Trial Schema, Flow diagram

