2.3 Potential Risks and Benefits

Benefits:

The primary benefit of participation in this study is more accurate identification of metastatic disease which may impact appropriate staging and therapy decisions. If occult metastasis are present but are not identified on conventional imaging this would lead to understaging and possible futile curative therapy. On the other hand, if conventional imaging identifies metastasis which are in fact false positive for neoplasia, and which could have been more definitively characterized by molecular imaging, this may lead to overstaging and inappropriate withholding of curative therapy.

Study Specific Procedure Risks:

1) Radiation Risks: The principal risk associated with a radiation dose is the possibility of developing a radiation-induced cancer later in life. However, the additional risk of radiation-induced cancer from these diagnostic procedures is low compared to the risks from the disease itself as well as systemic therapy or radiation therapy.

Human dosimetry data for fluciclovine from FDA package insert: The (radiation absorbed) effective dose resulting from the administration of the recommended activity of 370 MBq (10 mCi) of fluciclovine is 8 mSv (22 microSv/MBq). For an administered activity of 370 MBq (10 mCi), the highest-magnitude radiation doses are delivered to the pancreas, cardiac wall, and uterine wall: 38 mGy, 19 mGy, and 17 mGy, respectively.

Human dosimetry data for Ga-PSMA from Joint EANM and SNMMI Procedure Guideline for Prostate Cancer Imaging: Version 1.0 [42]. Based on the available studies, the coefficient for effective dose from ⁶⁸Ga-PSMA averages is 2.0×10^{-2} mSv/MBq, resulting in an average effective radiation dose of 3 mSv for an administered activity of 150 MBq. For a typical dose of 5 mCi (185 MBq) that we will be administering, the effective dose equivalent would be 3.7 mSv. The organs with the highest dose are urinary bladder wall (0.13-0.173 mSv/MBq) and kidney (0.122-0.262 mSv/MBq).

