2) Allergic or other reactions to radiotracer: Although the risk is extremely small, it is possible to develop an allergic reaction to the fluciclovine or Ga-PSMA. This can result in hives, rash, itching and difficulty breathing which may require emergency medical treatment. There have been no previous instances of allergic reaction. In prior studies with both radiotracers, the risk of adverse events which can be attributed to the radiotracer is extremely low, and of minimal medical impact such as burning at IV site or dysgeusia.

3) Risk related to IV for PET scan: A small amount of radioactive material will be injected by either a hand-held needle or a machine. Such injections are generally quite safe, but any injection involves some risks. The injection could harm a nerve, artery or vein, or cause infection. The radioactive material could also leak from veins, causing swelling and discomfort.

4) False positive on PET: It is possible that a lesion identified on the experimental PET procedures may be false positive, thus potentially leading to an inappropriate change in stage. Yet, no lesion will be acted upon which could change therapeutic intent unless confirmed via histology or advanced imaging such as MR for certain bone lesions. See below for risks associated with biopsy or MR.

Non-Study Specific Procedure Risks:

1) Biopsy associated risk: If a suspect lesion is identified on either or both PET scans, definitive histologic proof in the safest manner possible will be sought if clinically indicated. Risks of biopsy, though small in expert hands, include bleeding, infection and even rarely death. Note that before biopsy is considered, careful scrutiny of the already obtained CT or MR will be undertaken to determine if an unsuspected anatomic correlate can be identified. This will then prompt a discussion between the patient and primary clinician on the benefits versus risks to definitively determine if a metastasis is present which could affect therapy. Biopsy will be undertaken in the least invasive manner possible as a standard of care procedure, reimbursed by third party payers.

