4.1 Overall Design

We will undertake a study with 20 patients with treatment naïve biopsy proven ILC who have either: a) clinical or imaging suspicion of metastatic disease; b) biopsy proven metastatic disease but in whom there is suspicion of an even greater tumor burden that could change therapy approach. All patients will be recruited from the Winship Glenn Family Breast Cancer Program at any Emory facility. All patients will undergo Ga PSMA PET followed at minimum of 10 hours (to allow for radiotracer decay) by fluciclovine PET. (This may also happen in the opposite order, in which case 20 hours after fluciclovine will be needed to allow for decay.) There is no need for randomization since each patient will undergo both imaging techniques, and the results will be interpreted blindly. Thus, radiopharmacy scheduling will dictate the order of the radiotracers to ensure the patient will undergo both imaging modalities in the shortest time frame. Two nuclear medicine physician co-investigators, [name], will independently interpret the 20 cases, each reading half (the other reading the other half) of the fluciclovine and PSMA images (to avoid bias in always reading the same type of imaging). The readers will be blinded to all imaging including the other PET. All suspicious lesions with nonphysiologic activity above background for locoregional spread and distant disease will be identified and rated for suspicion of malignancy on a 6 point Likert scale (where 1 = definitely benign and 6 = definitely malignant). Both the primary lesion and all suspected metastases will be measured on an advanced workstation and metabolic uptake parameters (SUV, MTV, TLA) recorded. After both studies have been interpreted blindly, the third nuclear medicine physician co-investigator, [name], will blindly interpret **deidentified** PET studies on every patient (alternating for a total of 10 each fluciclovine and Ga-PSMA PET). Afterward, an unblinded reconciliation interpretation will take place with all 3 readers. To ensure balance, 10 of the studies will be reviewed for consensus first showing Ga-PSMA, then fluciclovine; 10 of the studies will be reviewed in the opposite manner. In this manner, a preliminary sense of kappa can be developed between the third and the other 2 readers, yet will guarantee the highest degree of patient care as there are currently no validated criteria for interpreting fluciclovine or PSMA PET for breast cancer. This approach will help us adapt existing prostate specific criteria to that of breast cancer. Concordant and discordant lesions between each PET study and conventional imaging will be reported and potential biopsy sites, if any, recommended. The most distant and accessible lesion may undergo biopsy in the safest manner possible (if not already done) as clinically indicated after discussion between the primary oncologist and patient.

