Adverse event data collection and reporting, which are required as part of every clinical trial, are done to ensure the safety of patients enrolled in the studies as well as those who will enroll in future studies using similar agents. Adverse events are reported in a routine manner at scheduled times during a trial (please follow directions for routine reporting provided in the full Data Safety and Monitoring Plan (DSMP)). Additionally, certain adverse events must be reported in an expedited manner for timely monitoring of patient safety and care. The following sections provide information about expedited reporting.

Special note for radiotracers given during this trial: The risk of AEs or SAEs from PET radiotracers is exceedingly low. A significant shift from baseline which can be attributable to the radiotracer injection and not the patient's medical condition will be considered an unexpected AE. An event greater than 20 hours post scan for fluciclovine and 10 hours for Ga-PSMA will not be considered a related to study procedure AE since the radiotracer has effectively decayed by 20 hours and 10 hours respectively. Reporting will follow relevant FDA and manufacturer guidelines as outlined below.

A serious adverse event is any medical occurrence which is fatal, is immediately life threatening, requires hospitalization (or prolongs an existing hospitalization), results in persistent significant disability or incapacity, is a congenital abnormality or a birth defect, or is considered medically significant by a physician.

The definition of serious adverse event (experience) also includes *important medical event*. Medical and scientific judgment will be exercised in deciding whether expedited reporting is appropriate in other situations, such as important medical events that may not be immediately life-threatening or result in death or hospitalization but may jeopardize the patient or may require intervention to prevent one of the other outcomes listed in the definition above. These should also usually be considered serious. Examples of such events are intensive treatment in an emergency room or at home for allergic bronchospasm; blood dyscrasias or convulsions that do not result in hospitalization; or development of drug dependency or drug abuse.

Attribution: The determination of whether an adverse event is related to a study imaging agent. The categories are:

Definite: The adverse event is clearly related to the study imaging agent.

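### Section 11 classes late adverse events as unrelated to the study procedure on decay grounds alone, although two listed procedure risks, infection and allergic reaction, do not depend on decay

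*Combined protocol and SAP*

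**What the plan says.** The special note for radiotracers in section 11 (Adverse Events) sets a fixed time limit on relatedness: "An event greater than 20 hours post scan for fluciclovine and 10 hours for Ga-PSMA will not be considered a related to study procedure" AE. It gives one reason: "since the radiotracer has effectively decayed by 20 hours and 10 hours respectively". No type of event is exempt.

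The same hours appear in section 4.1 as the minimum spacing between the two scans: 10 hours after Ga-PSMA and, in the reverse order, "in which case 20 hours after fluciclovine will be needed to allow for decay". Section 1.2 describes the spacing as "separated by at least 10 half-lives to allow for radioactive decay".

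Section 2.3 lists, under "Study Specific Procedure Risks", what the study procedures might cause. On allergy it says "it is possible to develop an allergic reaction to the fluciclovine or Ga-PSMA". Its paragraph on the IV names infection as a possible result of the injection.

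Section 11 also contains an ordinary attribution scheme: five categories from Definite to Unrelated, and a Step 3 at which relatedness to the imaging agent is decided. Neither mentions elapsed time. Section 4.4 and footnote e of section 1.3 provide for a nurse's call at 5-10 business days to ask about adverse events; section 4.4 gives its purpose as picking up delayed ones.

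**The concern.** The cut-off measures how long the tracer stays radioactive. The rule uses it to decide whether an event was caused by the study procedure. That is sound only for harms that need residual radioactivity at the time they begin. Infection arises from the needle or line, and allergy from the substance injected. Neither mechanism stops when the isotope decays.

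At stake is the accuracy of the recorded relatedness of late-onset events. If a patient developed an injection-site infection or an allergic reaction after the cut-off, the investigator following section 11 would have to record it as not related to the procedure, whatever the clinical picture suggested. Section 11 itself says adverse event data also serve patients in future studies of similar agents, and section 4.2 presents this pilot as groundwork for a definitive trial. The record should therefore reflect a judgement and not a preset.

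**Working it through.** The plan has no figure to reproduce here, and the point rests on no sample size or error rate. The check is a comparison of the sections.

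1. **What the rule covers.** Every event later than 20 hours (fluciclovine) or 10 hours (Ga-PSMA) after the scan. I read the time as time of onset, which is the reading kinder to the plan. The rule refers to the study procedure, which includes the IV injection.

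2. **What the rule rests on.** Decay only. That the same hours serve as the scan spacing in section 4.1, also justified there by decay, confirms that the cut-off is a radioactivity criterion.

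3. **The listed risks set against that ground.**

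| Risk in section 2.3 | Source of harm | Depends on decay? | Could begin after the cut-off? |
|---|---|---|---|
| Infection | The injection | No | Plausibly; no onset time given |
| Allergic reaction | The substance injected | No | Plausibly; no onset time given |
| Harm to nerve, artery or vein; leakage | The injection | No | Would normally begin earlier; not relied on |

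   The first two rows carry the point. The last column is inference. The column on decay follows from what each harm is.

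4. **The rule set against the attribution scheme.** The scale and Step 3 leave relatedness to be judged, with no time criterion. The special note removes that judgement for late events. The scale's wording names only the imaging agent, whereas the note speaks of the procedure. Giving the agent is the procedure, so one late event could be judged possible or probable on the scale and be unrelated under the note. Section 2.3 already treats an injection-site complaint as attributable to the tracer, giving "burning at IV site or dysgeusia" as examples, so the plan itself does not keep agent and injection apart.

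5. **Where this bites.** The call at 5-10 business days falls after both cut-offs. Events found on it that began before the cut-off are unaffected. Those that began after it are already classed as unrelated.

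6. **What does not change.** From sections 11 and 3.2:
   - Expedited reporting is triggered by grade and expectedness.
   - All SAEs go to the IRB.
   - FDA safety reports depend on seriousness and expectedness.
   - Ga-PSMA SAEs within 7 days go to the manufacturer whatever their apparent cause, disease progression excepted.
   - No endpoint concerns safety.

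7. **Exposure.** 20 patients × 2 tracers = at most 40 injections. No adverse event rate is given, so the number of affected events cannot be calculated. Section 2.3 calls attributable risk extremely low and reports no earlier allergic reaction.

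**The case against.** **The note is meant for the tracer alone.** It is headed for radiotracers and opens on their low risk, so this intent is arguable. It does not cure the mismatch: the rule's own words refer to the study procedure, and allergy to the tracer is itself independent of decay.

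**A specific note may supplement a general scale.** This is fair. The scale is silent on time, so adding a time rule is not a contradiction in form. The objection is to the ground for the rule, which does not fit two of the risks the plan lists.

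**Onset after the cut-off is undocumented.** This stands as a limit. It is a modest inference, not a fact in the documents.

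**Little follows from it.** This also stands, and it rules out several stronger readings:

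- A reader might infer that serious events would go unreported. The reporting routes listed above do not, for the most part, depend on relatedness, and late events are still collected.
- A reader might infer that the delayed-event call, the contact numbers in section 12 and the Principal Investigator's duty to evaluate reports contradict the rule. These provisions concern collecting and reporting events, not attributing them, and can coexist with a fixed attribution rule.
- A reader might infer an effect on the annual report to the Ga-PSMA manufacturer, which notes attribution to the kit. That follows only if the rule is also applied to the agent, and no section says it is.
- A reader might infer a bias in a procedure-related event rate. Section 10 plans no such analysis.
- A reader might cite the radiation-induced cancer risk in section 2.3 as a late harm that the rule misses. Such an event is not expected within adverse event follow-up, so it adds nothing practical.

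**Conclusion.** The concern holds in a limited form. As written, section 11 would misrecord the relatedness of an infection or allergic reaction that began after the cut-off and was in fact due to the injection or the tracer. It would do so automatically, in place of the attribution scale that the same section provides.

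The size is small and cannot be given as a number: at most 40 injections, no stated event rate, and few events expected. The effect stops at recorded relatedness. It does not reach the collection of events, most serious or expedited reporting, or any endpoint.

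The conclusion assumes that the study procedure includes the injection, that the cut-off is applied to time of onset, and that infection or allergy can begin after 10 or 20 hours. The documents support the first by their wording; the other two are readings stated here as assumptions. The point is worth correcting because the inconsistency is plain and the correction is cheap.

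**What to change.** Reconcile the special note in section 11 with the risk list in section 2.3 and with the attribution scale and Step 3. Either delete the automatic 20-hour and 10-hour exclusion, or confine the decay argument to acute radiation effects.

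In both cases, attribute late adverse events found up to and including the follow-up call on the existing Definite-to-Unrelated scale, with elapsed time since injection as one consideration. Add one sentence saying that the scale covers the injection as well as the agent. This is a clarification: section 2.3 already treats an injection-site complaint that way, but the scale's wording names only the agent.

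The cost is a wording change in section 11, with no new visit, procedure or data item. The downside is that a few more events may be classed as possibly related.

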APPENDIX A Abbreviations and definition of terms

The following abbreviations and special terms are used in this study Clinical Study Protocol.

Abbreviation or special term	Explanation
AE	Adverse event
Akt	Protein kinase B (or PKB)
CRFs	Case Report Forms
CT	Computed tomography
CTCAE	Common Terminology Criteria for Adverse Event
ctDNA	Circulating tumor DNA
DSMB	Data Safety Monitoring Board
DSMC	Data and Safety Monitoring Committee
DSMP	Data Safety and Monitoring Plan
ECOG	Eastern Cooperative Oncology Group
eCRF	Electronic case report form
ESR1	Estrogen Receptor alpha
FCBP	Female of childbearing potential
FDG	fluorodeoxyglucose
FDA	Food and Drug Administration
FSH	Follicle-stimulating hormone
GCP	Good Clinical Practice
hCG	Human chorionic gonadotropin
HIPAA	Health Insurance Portability Accountability Act
ICF	Informed consent form
IDC	invasive ductal carcinoma
IHC	Immunohistochemistry
IL	Interleukin
ILC	Invasive lobular carcinoma

Abbreviation or special term	Explanation
IMC	invasive metaplastic carcinoma
IND	Investigational New Drug
IRB	Institutional Review Board
ISCR	individual single case report
IV	Intravenous
MBq	Megabecquerel
mCi	Millicurie
MRI	Magnetic resonance imaging
NCCN	National Comprehensive Cancer Network
NCI	National Cancer Institute
NIH	National Institutes of Health
PET	Positron Emission Tomography
PI3Ks	Phosphoinositide 3-kinases
PSMA	Prostate specific membrane antigen
RNA	Ribonucleic acid
SAE	Serious adverse event
SUV	Standardized uptake value
TLA	Total lesion activity
VEGF	Vascular endothelial growth factor
